## 3 Statistical Methods

### 3.1 General Considerations

All data will be provided in data listings. Tabular summaries for limited efficacy and safety parameters in the double-blind treatment period will be presented by treatment group.

All efficacy data will be summarized using the analysis visits. The analysis visit windowing rules will be defined based on study days of post-baseline. The details of analysis visit windowing rules will be described in Section 3.4.

Day 1 will be defined as the day of first investigational product administration. For any variable, unless otherwise defined, the baseline value is the last non-missing assessment taken prior to the first

investigation product administration. The change from baseline will be calculated by subtracting the baseline values from the individual post-baseline values. If either the baseline or post-baseline value is missing, the change from baseline is set to missing.

The following conventions will be applied to all data presentations and summary.

- For continuous endpoints, arithmetic mean, and median will be formatted to one more decimal place than the measured value. SD will be formatted to two more decimal place than the measured value. Minimum and maximum values will be presented with the same number of decimal places as the measured value.
- For categorical variables, the count and percentage of responses will be presented in the form XX (XX.X%) where the percentage is in the parentheses.
- Data analyses will be conducted using SAS® version 9.4 (SAS Institute Inc., Cary, NC) or higher.

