**Table 3-2 Missing Dates Imputation Rules**

	Missing	Imputation	Exception
Start date (Adverse Events and concomitant medication)	Day	01	Default to Study Day 1 if an event starts the same year and month as Study Day 1 and Stop date is after Study Day 1
	Day/Month	01JAN	Default to Study Day 1 if an event started the same year as Day 1 and Stop date is after Study Day 1
	Day/Month/Year	No imputation	
Stop date (concomitant medication)	Day	Last day of the month	Default to the End of Study Date or the primary analysis cut-off date for ongoing subjects if the concomitant medication stopped the same year and month as the End of Study Date or primary analysis cut-off date
	Day/Month	31DEC	Default to the End of Study Date or the primary analysis cut-off date for ongoing subjects if the concomitant medication stopped the same year as the End of Study Date or primary analysis cut-off date
	Day/Month/Year	No imputation	

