#### **3.8.1.1 Pre-treatment AEs**

The AEs with onset prior to the administration of the first dose of investigational product (MEDI2070 or placebo) will be considered as pre-treatment AEs for the DB treatment period. Pre-treatment AEs will be listed with a flag.

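### Read literally, the final SAP's partial-date rule gives an ongoing adverse event that began in the month (or year) of first dose a pre-dose onset and drops it from the TEAE tables

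*Combined protocol and SAP*

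**What the plan says.** Final SAP Section 3.3.1 applies Table 3-2 in the analysis; listings show partial dates unaltered. The start-date rows cover adverse events and concomitant medication together. A missing day becomes 01, a missing day and month becomes 01JAN, and a wholly missing date is left alone. The missing-day exception substitutes Study Day 1 "if an event starts the same year and month as Study Day 1 and Stop date is after Study Day 1". For a missing day and month it reads "Default to Study Day 1 if an event started the same year as Day 1 and Stop date is after Study Day 1". The stop-date rows cover concomitant medication only.

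Section 3.1 fixes the reference date: "Day 1 will be defined as the day of first investigational product administration". Section 3.8.1.1 then states: "The AEs with onset prior to the administration of the first dose of investigational product (MEDI2070 or placebo) will be considered as pre-treatment AEs". The only output for these is a listing: "Pre-treatment AEs will be listed with a flag". Section 3.8.1.2 defines a TEAE by onset on or after the first blinded dose. Section 3.8 limits double-blind safety summaries to TEAEs and laboratory data.

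Table 3.3.1-1 of the pre-termination SAP has the same exceptions.

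**The concern.** The exception appears meant to keep an event that persists beyond first dose from being dated before it. Its test, however, is a stop date later than Study Day 1, and an event that never resolved has none. The rule therefore protects events that ended and fails those that did not.

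The error runs one way, since it can only remove events from the TEAE tables. It falls on unresolved events, and TEAE counts are among the few results the final SAP still tabulates. Blank stop dates are to be expected: under protocol Section 5.4.2, events unresolved at the last assessment are followed without further eCRF recording. A pre-dose imputed onset would not look odd either, because Section 5.4.1 collects adverse events from informed consent.

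**Working it through.** The plan gives no figure to reproduce. The check applies Table 3-2 literally and then counts.

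**One event, two outcomes.** Suppose Study Day 1 is 15 March, true onset is 20 March, and only the month of onset is recorded.
- Stop date 2 April: the exception is met, the imputed onset is 15 March, and the event is a TEAE.
- Ongoing: the exception is not met, the imputed onset is 1 March, and the event is pre-treatment.

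**No other section rescues it.** Final SAP Section 3.5.4 counts medications with missing start and stop dates as concomitant; adverse events have no such default. Protocol Section 4.8.5.1 also treats pre-dose events that worsen after dosing as treatment-emergent, but final SAP Section 3.8.1.2 omits that clause.

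**How often, given a missing day.** Assumptions, not in the documents: Day 1 is uniform over a 365-day year, and onset is uniform over 28 weeks (196 days, the double-blind period) or 52 weeks (364 days, last blinded dose at Week 24 plus 28 weeks). All events counted are truly post-dose and ongoing.
1. If Day 1 is day j of an m-day month, m − j + 1 onset days remain in that month. Over all j this sums to m(m + 1)/2.
2. Over the year: 7 × 496 + 4 × 465 + 406 = 5,738 combinations of Day 1 and onset day.
3. No error arises when Day 1 is the 1st. Those cases number 365, so 5,738 − 365 = 5,373 are misclassified, and 5,373/5,738 = 93.6%.
4. In any later month the 1st falls after Day 1, so the error is 0%.
5. As a share of all missing-day ongoing events: 5,373/(365 × 196) = 7.5% for 28 weeks and 5,373/(365 × 364) = 4.0% for 52 weeks.

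**How often, given a missing day and month.**
1. Onsets in the calendar year of Day 1, 28 weeks: 170 × 196 + 195 × 196/2 = 52,430. Removing the 196 with Day 1 on 1 January leaves 52,234. That is 99.6% of these events, and 52,234/71,540 = 73% of all such events.
2. 52 weeks: 2 × 364 + 363 × 364/2 = 66,794. Removing 364 leaves 66,430. That is 99.5% of these events, and 66,430/132,860 = 50% of all such events.

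**Leverage of one event.** Final SAP Section 1 gives 29 randomized subjects. If the planned 2:1:2:2:2 ratio held, arms average 29 × 2/9 = 6.4, with 29/9 = 3.2 in the low arm. One subject is then 1/6.4 = 16 or 1/3.2 = 31 percentage points. Actual arm sizes are not stated.

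**After the change.** Counting an ongoing event as meeting the stop-date condition brings every misclassification rate above to 0%.

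**The case against.** The strongest reply is that this is an ambiguity. An event still ongoing at last assessment cannot have stopped by Day 1, so a programmer could sensibly treat it as meeting the condition. The separate statistical programming plan may say so. This stands as far as it goes: the documents do not show that any event was misclassified. But neither SAP says that a blank stop date qualifies, and the literal reading gives the wrong result.

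The consequence is also bounded. Section 3.8.1 lists all adverse events, pre-treatment ones are flagged, Section 3.8.2 lists deaths and discontinuations due to adverse events by group, and Section 3.8 makes no statistical comparison. Section 3.8.1 also counts a specific event once per subject, so a lost record changes a row only if that subject has no other qualifying record there. All of this stands. It limits the harm to the tables without correcting them.

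A reader might infer more than the text supports in three ways:
- That every ongoing event with a missing start day is lost. With a missing day, the error is confined to the calendar month of first dose.
- That a partial stop date can never meet the exception. With Day 1 on 15 March, a stop recorded only as April of that year is already after Day 1. Only stops whose known part does not settle the order are unclear.
- That every ongoing event in the exposed month is wrongly classed. Some began between consent and dosing, and for those pre-treatment is correct.

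**Conclusion.** The defect holds for a narrow class: adverse events with no stop date and a start date known only to the month, or only to the year, of Study Day 1. Followed literally, Table 3-2 dates them before dosing unless Day 1 is itself the imputed date. For a missing day, that exempts 12 of 365 possible dates, leaving 353/365 = 96.7% exposed. Among truly post-dose events in the class, the error is 93.6% for a missing day and over 99% for a missing day and month, under the uniform-date assumptions.

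The number of such events is not given, is probably small and could be zero. A reader might take the 16- and 31-point figures as the expected distortion. They are only the effect of one lost subject-event if the planned allocation ratio held. The point is worth correcting because the rule errs in one direction, affects one of the few remaining summaries, and is cheap to change. It does not show that the safety tables are wrong.

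**What to change.** Amend both exceptions in final SAP Table 3-2, for adverse events only. Impute Study Day 1 when the known part of the start date matches Study Day 1 and any one of these holds: the event is ongoing; its stop date is missing; or the known part of its stop date does not place it before Study Day 1.

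Split the shared start-date row so that the concomitant-medication rule is unchanged. Otherwise ongoing background medication with a partial start date would be reset to Day 1 and cease to count as prior medication under Section 3.5.4. The superseded pre-termination SAP needs no edit.

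The cost is a short table edit and one programming change. Some ongoing events that truly began before dosing in that month or year will be counted as treatment-emergent. That is the conservative direction for safety, and it matches how the table already treats events with a stop date after Day 1. An event with a partial start date that stopped on Day 1 itself would also become treatment-emergent.

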#### 3.3.2 Missing Baseline Evaluation

For any endpoint, unless otherwise defined, the baseline value is the last non-missing assessment taken prior to the first investigational product administration. If the baseline is still missing following above definition, the baseline evaluation will not be imputed and will be considered as missing.

### 3.3.3 Missing Efficacy Evaluations

Through the end of the DB period (induction and maintenance periods), the missing efficacy data will be handled as described below:

- Missing data for dichotomous endpoints will be handled using the non-responder imputation method, i.e. any subject with missing information on the endpoint will be assumed as a non-responder.
- Missing data for continuous measures will not be imputed.
- Missing data for PRO components (e.g. IBDQ, CD-PRO) will be handled according to the scoring algorithm as described in corresponding sections. If the score is still missing, no further imputation will be done.

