##### **4.7.1 Permitted Concomitant Medications**

Investigators may prescribe concomitant medications or treatments deemed necessary to provide adequate supportive care except for those medications identified as “excluded” as listed in Section 4.7.2. Specifically, subjects should receive full supportive care during the study, including transfusions of blood and blood products, and treatment with antibiotics, anti-emetics, antidiarrheals, and analgesics, and other care as deemed appropriate, and in accordance with their institutional guidelines.

In addition, the following concomitant medications for CD are permitted during the study:

- 5-aminosalicylates, only if being taken at baseline
- Prednisone up to 20 mg/day or equivalent, only if being taken at baseline
- Budesonide up to 9 mg/day, only if being taken at baseline
- Azathioprine, only if being taken at baseline
- 6-mercaptopurine, only if being taken at baseline
- Methotrexate, only if being taken at baseline

- Oral antibiotics for CD (except for the treatment of acute illness), only if being taken at baseline
- Probiotics (eg, Culturelle and *Saccharomyces boulardii*), only if being taken at baseline
- Antidiarrheals (eg, loperamide and diphenoxylate with atropine) for control of chronic diarrhea, only if being taken at baseline

The investigator may not increase the subject's dose of the permitted concomitant medications listed above, and may not initiate treatment with any of these medications after the deadlines specified in the inclusion criteria, Section 4.1.2, criterion #6.

The dose of the medications listed above may not be reduced during the subject's study participation before the Week 16 assessments, including ileocolonoscopy, have been completed, with the exception that antidiarrheal agents may be stopped if the subject has had no stools in 3 consecutive days. After any such stopping of antidiarrheal agents during the double-blind period, if any recurrence of loose stools occurs prior to Week 8, antidiarrheal use should be immediately resumed.

Subjects receiving oral corticosteroids should initiate oral corticosteroid tapering as per local standard of care if, after Week 16, they have achieved both:

- SES-CD response (see Section 2.2), AND
- PRO2 response (see Section 2.2)

For assessment of the SES-CD score for the purpose of tapering oral corticosteroid therapy, the investigators' own scoring of these results may be used in place of central scoring.

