##### **4.8.4.1 Primary Efficacy Analysis**

The primary analysis will be conducted in the ITT population. The primary efficacy endpoint is CDAI remission at Week 8 of the induction period. The primary comparison of interest will be MEDI2070 high dose group versus placebo. The comparisons between MEDI2070 high-medium dose group versus placebo, low-medium dose group versus placebo, and MEDI2070 low dose group versus placebo will also be conducted.

Missing data will be handled using the non-responder imputation method through the end of the placebo-controlled, double-blind period; ie, any subject with missing information on the primary endpoint will be assumed as a non-responder. In addition, subjects with a clinically meaningful increase in steroid use will also be assumed to be non-responders for the primary analysis perspective. Clinical meaningful increase in steroid dose is defined as an increase of at least 5 mg/day for at least 3 days of prednisone, or equivalent, or an increase of at least 3 mg/day for at least 3 days of budesonide.

The difference in CDAI clinical remission rates at Week 8 between MEDI2070 dose groups and placebo group and associated 90% confidence interval will be provided. P-values for comparisons between any MEDI2070 dose group and placebo will be obtained from a logistic regression model adjusting for the number of prior anti-TNF $\alpha$  agents that failed or were not tolerated (1 vs > 1). In the event the number of remissions is too small (ie, < 5), the exact logistic regression will be performed instead. The statistically significant treatment effect will be tested against two-sided alpha level of 0.10.

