#### **4.8.4.3 Secondary Efficacy Analyses**

##### **Double-blind Induction and Maintenance Periods**

The efficacy endpoints from the placebo-controlled, double-blind, induction and maintenance periods will be summarized descriptively and displayed graphically by visit and by treatment using the ITT population. The secondary efficacy endpoints with dichotomous outcomes from double-blind, induction and maintenance periods will be analyzed in a similar way to the primary efficacy endpoint.

The dose-response analysis may be repeated for secondary endpoints in the double-blind, induction period, including but not limited to SES-CD remission and response at Week 16, PRO2 remission and response at Week 8 and Week 16, CDAI response at Week 8 and Week 16, and CDAI clinical remission at Week 16.

[REDACTED]

[REDACTED]

[REDACTED]

[REDACTED]

[REDACTED]

[REDACTED]

[REDACTED]

[REDACTED]

[REDACTED]

[REDACTED]

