### 3.4 Analysis Visit Windowing Rules

The actual visit for a subject may not exactly coincide with their targeted visit date. The actual visit date will be mapped to the study visit following the analysis visit windowing rules below. Unless specified otherwise, all efficacy and safety analyses will be based on the analysis visits. If there are multiple records fall within the same defined analysis visit window, the non-missing record closest to the target day will be considered for the analysis.

If two non-missing assessment actual dates are equidistant from the target day, the later visit will be considered for analysis.

Composite endpoints (e.g. CDAI score) will be calculated for each date at which individual components are being measured before applying the analysis visit windows rather than to calculate visit window based individual component.

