#### **3.6.1.3 Additional Analyses of the Primary Efficacy Endpoint**

No sensitivity analyses of the primary efficacy endpoint will be performed.

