### 3.6.2.2 Secondary Efficacy Analyses

The efficacy data from the DB induction and maintenance periods will be summarized descriptively by treatment group and by visit using the ITT Population.

The secondary efficacy endpoints with dichotomous outcomes will be summarized similarly as the primary analysis of the primary efficacy endpoint using the ITT population.

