### 3.3.3 Missing Efficacy Evaluations

Through the end of the DB period (induction and maintenance periods), the missing efficacy data will be handled as described below:

- Missing data for dichotomous endpoints will be handled using the non-responder imputation method, i.e. any subject with missing information on the endpoint will be assumed as a non-responder. In addition, subjects with a clinically meaningful increase in steroid use will also be assumed to be a non-responder for the primary

analysis perspective. Clinical meaningful increase in steroid dose is defined as an increase of at least 5 mg/day for at least 3 days of prednisone, or equivalent, or an increase of at least 3mg/day for at least 3 days of budesonide.

- Missing data for continuous measures will not be imputed. The continuous measures will be analyzed using the repeated measure mixed effects model adjusting for prior anti-TNF $\alpha$  agent use and baseline covariate, assuming the missing at random mechanism. Other missing data imputation method (e.g. multiple imputation) may be explored.
- Missing data for PRO components (e.g. IBDQ, CD-PRO) will be handled according to the scoring algorithm as described in corresponding sections. If the score is still missing, no further imputation will be done.

Through the end of the OL period, the missing efficacy data will be handled as described below:

- Missing data for dichotomous endpoints will be handled using the non-responder imputation method in a similar way of the DB period.
- Missing data for continuous measures will not be imputed and will be summarized as observed.
- Missing data for PRO components (e.g. IBDQ, CD-PRO) will be handled in the same way as the DB period.

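### The final SAP drops, without giving a reason, the protocol rule that a clinically meaningful steroid increase makes a subject a non-responder at Week 8

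*Combined protocol and SAP*

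**What the plan says.** Protocol 4.8.4.1 first counts a subject with missing primary-endpoint information as a non-responder. It then adds that "subjects with a clinically meaningful increase in steroid use will also be assumed to be non-responders for the primary analysis perspective". An increase qualifies if it lasts at least 3 days and is at least 5 mg/day of prednisone or equivalent, or at least 3 mg/day of budesonide.

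The original SAP, section 3.3.3, carries both parts forward: "subjects with a clinically meaningful increase in steroid use will also be assumed to be a non-responder for the primary" analysis, with the same thresholds.

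The final SAP, section 3.3.3, has the missing-data part only: "Missing data for dichotomous endpoints will be handled using the non-responder imputation method, i.e. any subject with missing information on the endpoint" becomes a non-responder. The bullet is a complete sentence with no redaction mark, and steroids are not mentioned.

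The final SAP still reports Week 8 CDAI remission in the ITT population, descriptively (3.6.1.2). Of additional analyses it says: "No sensitivity analyses of the primary efficacy endpoint will be performed".

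**The concern.** The endpoint is CDAI below 150 at Week 8 in every version. The steroid clause is a separate rule about who may be credited with reaching it: a subject whose score fell after extra steroid is not counted as a success of the assigned treatment. Without the clause, the final SAP can report as a remitter someone whom the protocol's primary analysis reports as a non-responder.

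The rule can only turn remitters into non-responders. Leaving it out can therefore raise an arm's remission rate or leave it unchanged, but cannot lower it. The direction of any bias between arms is unknown, because nothing in the documents says in which arms increases occurred.

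The remission table would carry no flag. The final SAP lists concomitant medications by subject (3.5.4), but it no longer includes the original SAP's by-visit summary of oral corticosteroid dose. A reader would have to match listings to find a case.

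**Working it through.** **Step 1: is the rule restored elsewhere in the final SAP?** The places where it could appear are:

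- 3.6.1.1, endpoint definition: CDAI below 150, with no steroid condition.
- 3.6.1.2, primary analysis: ITT population, descriptive summary only.
- 3.6.1.3, additional analyses: none.
- Appendix 6.1, CDAI scoring rules: diary completeness, missing items and negative totals only.
- 3.5.2, baseline characteristics: corticosteroid use at baseline, which does not capture an increase.

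No readable text restores it.

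**Step 2: does early termination explain the omission?** Section 2 cites the small number of subjects as the reason for giving descriptive statistics on limited endpoints. The same reason is repeated where the biomarker, dose-response, open-label efficacy and subgroup analyses are dropped (3.6.2.3, 3.6.4.1, 3.6.4.2, 3.6.5). Small numbers justify removing tests and models. They do not bear on which subjects count as remitters, and responder classification is still in use because missing still means non-response.

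**Step 3: can an affected subject have a Week 8 score?** Protocol 4.3.1.1 has CDAI assessed at each study visit from Visit 2. Final SAP 3.4 says "The actual visit date will be mapped to the study visit following the analysis visit windowing rules below" and, if several records fall in a window, uses the non-missing one closest to the target day. A score recorded after a steroid increase can therefore become the Week 8 value. The window limits are redacted, so how often this could happen cannot be assessed.

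**Step 4: size of one reclassification.** No figure in the plan is computed from the steroid rule, so the inputs are the 29 subjects randomized (final SAP 1) and the ratio 2:1:2:2:2, whose parts sum to 9 (final SAP 2.4).

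Check of the ratio against the planned arm sizes: 342 × 2/9 = 76 and 342 × 1/9 = 38, as stated.

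Expected arm sizes at termination:

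- Larger arms: 29 × 2/9 = 6.44, so 6 or 7 subjects.
- Low-dose arm: 29 × 1/9 = 3.22, so 3 or 4 subjects.

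Shift in an arm's rate for one affected subject is 1/n:

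| Arm | n | Shift (percentage points) |
|---|---|---|
| Larger | 7 | 1/7 = 14.3 |
| Larger | 6 | 1/6 = 16.7 |
| Low dose | 4 | 1/4 = 25.0 |
| Low dose | 3 | 1/3 = 33.3 |

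For scale, the study was sized to detect 31% − 12% = 19 points between high dose and placebo. With no affected subject the shift is 0.

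**The case against.** The strongest reply is that the case will hardly ever arise.

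- Protocol 4.7.1 bars the investigator from increasing the "dose of the permitted concomitant medications listed above, and may not initiate treatment with any of these medications" after the stated deadlines.
- Protocol 4.1.6 stops investigational product when recurrent symptoms warrant escalation.
- The note to file in Appendix 6.3 of the final SAP records that follow-up visits could not be entered in the device for withdrawn or early-terminated subjects until a workaround in December 2017. A subject escalated and terminated before Week 8 would often have no Week 8 CDAI and would already be a non-responder under the missing-data rule.
- A prohibited increase may also appear in the listing of critical and major deviations (final SAP 3.5.8).
- The protocol's general statements of non-responder imputation (synopsis, 4.8.1) mention missing data only.
- A separate programming plan, not among these documents, might apply the rule.
- The analysis is descriptive, for 29 subjects whose data are all listed.

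Most of this is correct, and it limits how often the omission matters. It does not remove the mismatch. The protocol contains the same conduct limits and still has the steroid rule, so its authors did not treat the limits as sufficient. Stopping product does not set an observed CDAI to missing. A subject who stays on study after an increase, or whose early termination visit maps to Week 8, can still be counted as a remitter. A deviation listing does not flag that subject in the remission table. Protocol 4.8.4.1 is the specific text for the primary analysis, and the original SAP followed it. A programming plan should implement a rule stated in the SAP, not supply one that is missing.

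**Conclusion.** The concern holds. The final SAP departs from the protocol's primary-analysis classification and gives no specific reason. A subject with a qualifying steroid increase and an observed Week 8 CDAI below 150 is classified differently by the two documents.

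The shift of about 14 to 17 points in a larger arm, or 25 to 33 in the low-dose arm, applies per affected subject and assumes arms close to the planned ratio. Actual arm counts are not given. The final ITT population requires at least one whole dose, so denominators could be smaller and the shift larger. The number of affected subjects is unknown and may be zero. No p-value, error rate or power figure is involved.

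This should be corrected because it concerns the primary endpoint and the correction is cheap, not because a large effect has been shown.

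**What to change.** In final SAP 3.3.3, restore the steroid rule and its thresholds from protocol 4.8.4.1 for the Week 8 primary endpoint. Neither the protocol nor the original SAP gives a time window for the increase, so say which increases count; up to the Week 8 assessment is the natural reading. Footnote the Week 8 remission table with the number of subjects the rule reclassifies in each arm, including zero if there are none.

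If the omission was deliberate, state and justify the departure from protocol 4.8.4.1, and list subjects with a qualifying increase before Week 8.

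Also state whether the rule applies to the secondary dichotomous endpoints. Protocol 4.8.4.3 says they "will be analyzed in a similar way to the primary efficacy endpoint", and final SAP 3.6.2.2 says: "The secondary efficacy endpoints with dichotomous outcomes will be summarized similarly as the primary analysis of the primary efficacy endpoint using the ITT population". Neither settles whether the steroid rule goes with them, since it is worded for the primary analysis.

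The cost is about two sentences plus the timing clause, one footnote, and a flag derived from concomitant-medication data already recorded and listed. A reported Week 8 rate would fall if any subject is reclassified.
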